## 12.5. Treatment Emergent Adverse Events of Special Interest

The TEAESI category groups include the following:

- Allergic alveolitis
- Haemoptysis
- Bronchospasm \*
- Exacerbation of underlying pulmonary disease \*
- Ototoxicity
- Nephrotoxicity
- Neuromuscular disorders

\* These TEAEs are additionally categorized by the Investigator. This judgment is listed but not summarized or used for identification of AESIs.

PTs for TEAESIs are listed as per [Appendix H](#), and additional PTs may be added during the study conduct.

The incidence will be summarized by each TEAESI category and PT by study treatment group.

## 12.6. Deaths

A listing of all AEs resulting in death will be provided.

## 12.7. Rescue Therapy

Rescue therapy is defined as any change from the randomized treatment (ALIS + background regimen or ELC + background regimen) as prescribed in the study (includes drug, dose, frequency, route of administration) due to progression of MAC lung infection. Rescue therapy does not include changes from randomized treatment (eg, removal or replacement of drug) due to intolerance or AEs from study drugs.

It should be noted that rescue therapy does not mean initiating a more efficacious treatment. Treatment options for MAC lung disease known to be efficacious other than (at a minimum) the combination of a macrolide plus ethambutol already provided in the study are limited. Furthermore, these patients are failing initial course of therapy and should be considered refractory; recommended treatment in that case would be the addition of ALIS – which may or may not have already been provided as part of randomized treatment. Therefore, rescue therapy is specifically initiation of alternative treatment due to progression of MAC lung disease because current treatment has failed.

Subjects who receive rescue therapy will stop randomized treatment (ALIS + background regimen or ELC + background regimen), be treated by local standard of care or as recommended by the Investigator and will continue with their remaining scheduled study visits.

Data is collected on the appropriate eCRF pages.

A summary of number and percentage of subjects with rescue therapy will be provided.

## 12.8. Nebulizer Deficiency

ALIS/ELC is administered to subjects by oral inhalation using the [REDACTED] nebulizer system. TEAEs related to device deficiency will be summarized and listed.

## 12.9. Clinical Laboratory Evaluations

Numeric laboratory parameters (hematology, chemistry (incl CRP), and urinalysis) will be summarized using descriptive statistics at baseline and at each post-baseline timepoint for the safety analysis set. Changes from baseline will also be summarized. Descriptive statistics at baseline and change from baseline is limited to continuous data.

Shift tables (ie, low-normal-high at baseline versus low-normal-high at follow-up in a 3-by-3 contingency table) will be provided to assess changes in laboratory values from baseline to post-baseline visits. Reference ranges established by the central laboratory will be used to determine shifts.

Clinical laboratory results will be provided in subject listings for the safety analysis set. Subjects experiencing ALT or AST  $\geq 3 \times$  ULN and total bilirubin  $> 2 \times$  ULN according to Hy's Law will be listed.

A summary of counts of subjects with an abnormal laboratory value at any visit including unscheduled will also be provided.

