- m. Sputum cultures will be collected by study personnel at in-clinic study visits prior to administration of study drugs. Subjects will provide and ship sputum cultures at non in-clinic visits. Subjects who are not able to ship sputum samples may bring the samples to the clinic site. Two sputum samples will be obtained from each subject at each assessment; subjects will produce 1 sputum sample on the day prior to the scheduled visit and 1 sputum sample on the day of the visit prior to dosing with study drugs. At Screening, subjects will produce 1 sputum sample on the first day of the visit and 1 sputum 1 week later. The second sputum sample provided at Screening can be produced any time during the week following the Screening visit.
- n. All laboratory testing should be performed prior to the administration of study drugs at in-clinic visits. Laboratory testing will **not** be performed at the Month 5 visit.
- o. A prior chest CT scan may be used as a subject's Screening measurement if this CT scan was obtained within 6 months from the subject's Screening visit. Subjects who do not have a chest CT scan within 6 months prior to Screening will be required to obtain a scan during Screening.
- p. Study drugs may be administered at home during a home care visit (if applicable), if administration at site is not feasible
- q. Study drugs may be dispensed directly to the subject's home by a courier if dispensing at site is not feasible

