## 7. GENERAL STATISTICAL CONSIDERATIONS

### 7.1. General

All summaries will be provided by treatment group; efficacy analyses will utilize randomized treatment (ITT analysis set), while safety will use treatments as received (Safety analysis set).

In case of misrandomization to incorrect strata, subjects will be analyzed as collected in CRF.

Methods of cross-sectional analyses and psychometric validation of PRO are described in the VAP.

Descriptive statistics for continuous variables include n, mean, SD, median, minimum, maximum, 1st quartile and 3rd quartile. Summaries of continuous variables that have some values recorded using approximate values (eg, < or >) will use the numeric part of the value in calculations. Listings will present the data in its original format.

Categorical variables will be tabulated by counts and by percentage of subjects in corresponding categories. Footnotes will specify the basis for the percentages. Category including missing assessments will be included if appropriate.

Data from unscheduled visits will not be used in summaries, except for the derivation of baseline and the summary of subjects with an abnormal laboratory value.

Listings corresponding to all summaries in this section will be provided. Listings will also include data from unscheduled visits.

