### 7.3. Baseline Definition

Unless otherwise stated, for the purpose of analysis baseline value is the last non-missing value prior or at the date of the first dose of ALIS/ELC, AZI or ETH, regardless of the visit in which it occurs including unscheduled visits.

Change from baseline will be calculated as:

- Change from baseline = post baseline value – baseline value

Ratio from baseline will be calculated as:

- Ratio from baseline = post baseline value / baseline value

Many assessments are done at Screening and Baseline/Day 1. For summaries, whenever baseline is presented, the above baseline definition is used. That is, the baseline summary presented is in general not the summary of the Baseline/Day 1 visit. Screening values will be listed but not summarized.

Throughout the document Baseline (capital B) refers to the visit Baseline/Day 1; baseline (lower case b) refers to the values derived using the baseline definition above.

The baseline MAC species/genome is the species grown in sputum samples collected at Baseline/Day 1. If Baseline/Day 1 is MAC culture negative or missing, the Screening samples will be taken instead (see [Section 9.3.7.1](#)).

Subjects being evaluated in this study have a diagnosis of MAC lung disease, as indicated by an investigator-reported positive MAC culture within 6 months of Screening, and a single sputum sample that is positive for MAC culture at Screening. For the purpose of descriptive summaries at Baseline, if culture assessment is negative at the Baseline visit, the baseline culture status will be regarded as the value at the screening visit.

For the purpose of actigraphy data analysis, baseline will be defined as data recorded in the period Day 8 – Day 14.

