**Table 8: Hearing Impaired CTC Grade**

Grade	Criteria
1	Threshold shift of 15 - 25 dB averaged at 2 contiguous test frequencies in at least one ear.
2	Threshold shift of >25 dB averaged at 2 contiguous test frequencies in at least one ear.
3	Threshold shift of >25 dB averaged at 3 contiguous test frequencies in at least one ear
4	Decrease in hearing to profound bilateral loss (absolute threshold >80 dB hearing loss at 2 kHz and above)

The baseline hearing test is the threshold for deriving the grade. Subjects who do not meet any of the above CTC grades will not be summarized.

The audiology results will be tabulated (number and percentage of subjects) by CTC grade (1, 2, 3, 4) within treatment and total groups. When presenting results, the highest CTC grade at a post-baseline visit (including unscheduled visits) will be used. The denominator for frequency calculation is the safety analysis set.

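### The abnormal-laboratory count in SAP 12.9 has no post-baseline limit, yet it is the only laboratory table that takes post-dose unscheduled results (minor)

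*SAP*

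**What the plan says.** SAP 12.9 (Clinical Laboratory Evaluations) plans descriptive statistics, change from baseline, three-by-three shift tables from baseline to post-baseline visits, subject listings and a Hy's Law listing. It then adds one more table: "A summary of counts of subjects with an abnormal laboratory value at any visit including unscheduled will also be provided".

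The general rule on unscheduled data is in SAP 7.1: "Data from unscheduled visits will not be used in summaries, except for the derivation of baseline and the summary of subjects with an abnormal laboratory". The second of these exceptions is the SAP 12.9 count. The same section adds: "Listings will also include data from unscheduled visits".

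SAP 7.3 defines baseline: "baseline value is the last non-missing value prior or at the date of the first dose of ALIS/ELC, AZI or ETH". It also states: "Screening values will be listed but not summarized".

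For audiology, SAP 12.12 (text below Table 8) is worded differently: "the highest CTC grade at a post-baseline visit (including unscheduled visits) will be used".

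On timing, a footnote to Protocol Table 4 (section 6.1) says: "All laboratory testing should be performed prior to the administration of study drugs at in-clinic visits".

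**The concern.** A safety count by arm should describe what happened after treatment began. Taken literally, this one makes a subject a case on the strength of a Day 1 or pre-dose unscheduled value alone. Such values are to be expected. Protocol 4.1.2 excludes AST or ALT only from 3 × ULN, bilirubin only from 1.5 × ULN and creatinine only above 2 × ULN, so subjects between the normal limit and those cut-offs can enter. Most of the other parameters in Protocol Table 5 have no entry limit.

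The shift tables and change-from-baseline summaries do take baseline into account, but SAP 7.1 keeps post-dose unscheduled results out of them. Scheduled post-dose draws are at Months 1, 3, 6 and 7 only. Protocol 6.1 sends any extra monitoring recommended by local labelling to unscheduled assessments. A creatinine rise seen only between Months 3 and 6, for example, would enter just one laboratory table, and that table mixes it with pre-dose abnormalities. Nephrotoxicity is a named adverse event of special interest, so the arm comparison is of interest.

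**Working it through.** The plan states no figure for this table, so there is nothing to reproduce. The check sets the rules side by side and then works out the dilution.

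**1. What each output uses**

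| Output | Post-dose unscheduled results | Baseline status |
|---|---|---|
| Change from baseline, shift tables (SAP 12.9) | No (SAP 7.1) | Used |
| Abnormal-value count (SAP 12.9) | Yes | Ignored |
| Audiology grade table (SAP 12.12) | Yes | Post-baseline only, graded against baseline |
| Listings (SAP 7.1) | Yes | Visible by subject, no arm count |

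The audiology wording shows that the SAP writes the post-baseline limit where it is meant. SAP 12.9 does not carry it.

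**2. Draws that can make a case.** Protocol Table 4 schedules 2 pre-dose draws (Screening, Baseline/Day 1) and 4 post-dose draws (Months 1, 3, 6, 7). Literally, 2 of 6 scheduled draws can create a case before any dose. If the SAP 7.3 rule on Screening values governs this table, it is 1 of 5. Day 1 stays in either way.

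**3. Dilution.** Let b be the share already abnormal before dosing, taken as equal in both arms, and e the incidence of a new post-dose abnormality among the rest. The table shows b + (1 − b)e per arm, so the arm difference is (1 − b)(e_ALIS − e_ELC). The documents give neither b nor e; all rates below are assumptions.

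| b | e = 12% vs 4% | Difference, ratio | e = 20% vs 5% | Difference, ratio |
|---|---|---|---|---|
| 0% | 12.0% vs 4.0% | 8.0 points, 3.0 | 20.0% vs 5.0% | 15.0 points, 4.0 |
| 10% | 20.8% vs 13.6% | 7.2 points, 1.5 | 28.0% vs 14.5% | 13.5 points, 1.9 |
| 20% | 29.6% vs 23.2% | 6.4 points, 1.3 | 36.0% vs 24.0% | 12.0 points, 1.5 |
| 30% | 38.4% vs 32.8% | 5.6 points, 1.2 | 44.0% vs 33.5% | 10.5 points, 1.3 |

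With 20% versus 5%, the share of ALIS cases already abnormal before dosing is b divided by the ALIS proportion: 0.10/0.28 = 36%, 0.20/0.36 = 56% and 0.30/0.44 = 68%.

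In subjects, at 50 per arm, the loss in the first scenario is 0.8, 1.6 or 2.4 points × 50 = 0.4, 0.8 or 1.2 subjects.

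**4. What the post-baseline limit does alone.** Let p be the chance, equal in both arms, that a subject abnormal at baseline is abnormal again afterwards. The limited count is bp + (1 − b)e. At b = 20% with 12% versus 4%:

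- p = 0: 0.8 × 12% = 9.6% versus 0.8 × 4% = 3.2%, ratio 3.0, difference 6.4 points.
- p = 1: 20% + 9.6% = 29.6% versus 20% + 3.2% = 23.2%, the same as the any-visit count.

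The limit removes subjects whose abnormality was only pre-dose. Only a split by baseline status recovers 12% versus 4%.

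**The case against.** The strongest reply is that little is lost. Scheduled shift tables, change from baseline, the Hy's Law listing and listings that include unscheduled data all remain. Protocol 9.9.2 requires laboratory abnormalities to be recorded as adverse events when they are clinically significant, come with signs or symptoms, need intervention or lead to stopping study drug, and it sets no scheduled-visit condition. SAP 12.4 and 12.5 tabulate these by arm, with nephrotoxicity as its own category, from first dose to 28 days after the last. SAP 7.3 arguably removes Screening values already. All SAP summaries are descriptive (SAP 7.2), and on the assumed figures the loss is about one subject per arm.

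Most of this stands, and it sets the severity. It also rules out two stronger readings that a reader might infer:

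- That this is the only summary in the SAP that uses unscheduled results. It is not: the audiology grade table uses them too, and unscheduled pre-dose values can serve as baseline.
- That the table hides drug-related laboratory changes. It dilutes one count; the outputs just listed would still show changes.

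The reply does not remove the defect. Protocol 9.9.2 also says that laboratory abnormalities are not usually recorded as adverse events, so the event tables cover only the clinically important part. Listings give no arm-level count. A descriptive table is read by comparing the arms, so it should count on-treatment abnormalities.

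**Conclusion.** The point holds as a minor one. By its wording, the SAP 12.9 count treats pre-dose abnormalities as equal to on-treatment ones, and under SAP 7.1 it is the only laboratory table with post-dose unscheduled results. The arm difference is multiplied by 1 − b, and the ratio moves further toward 1. The factor follows from the definition of the count, given equal b in both arms. Its size is unknown, because the documents give no baseline abnormality rate and the entry limits show only that such values are permitted. SAP 12.9 also does not say whether the count is per parameter; pooled over parameters, b could only be as large or larger. Whether Screening values count is unclear, but the Day 1 draw is enough for the conclusion.

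**What to change.** 1. In SAP 12.9, limit the count to post-baseline visits, scheduled and unscheduled, in line with SAP 12.12.
2. Present it by parameter and direction (low, high) and by baseline status: not abnormal in that direction at baseline, or already abnormal. Subjects abnormal at baseline are then shown on their own line and not dropped. Use as denominator the subjects in each baseline group with at least one post-baseline value.
3. Add a shift table from baseline to the worst post-baseline value in each direction, including unscheduled visits.
4. In SAP 7.1, name this shift table and the audiology grade table as further exceptions, since SAP 12.12 already departs from the rule as written.

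The cost is SAP wording, one revised table and one added table, with no new data. One limit remains: low/normal/high categories do not show worsening within the abnormal range, so for unscheduled values that would still have to be read from the listings.

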### 12.10. Vital Signs

Systolic and diastolic blood pressure, heart rate, respiratory rate, oxygen saturation, temperature, height, and weight will be collected at protocol-specified visits.

Descriptive summaries of actual values and changes from baseline will be based on available data and will be provided by visit.

### 12.11. Physical Examination

Any abnormalities observed at Screening will be recorded in the medical history or as AEs if they occur after randomization.

Dates of Physical Examinations will not be listed.

### 12.12. Audiology Tests

Audiology testing will be performed at the protocol-specified visits. Frequencies of 250, 500, 1000, 2000, 4000, and 8000 Hz will be evaluated for each ear using air conduction.

The actual, baseline, and change from baseline audiology test results will be summarized descriptively by visit, frequency, and ear.

In addition, the data will be summarized by subjects who meet CTCAE v5.0 grading criteria for hearing impairment included in [Table 8](#):

**Table 8: Hearing Impaired CTC Grade**

Grade	Criteria
1	Threshold shift of 15 - 25 dB averaged at 2 contiguous test frequencies in at least one ear.
2	Threshold shift of >25 dB averaged at 2 contiguous test frequencies in at least one ear.
3	Threshold shift of >25 dB averaged at 3 contiguous test frequencies in at least one ear
4	Decrease in hearing to profound bilateral loss (absolute threshold >80 dB hearing loss at 2 kHz and above)

The baseline hearing test is the threshold for deriving the grade. Subjects who do not meet any of the above CTC grades will not be summarized.

The audiology results will be tabulated (number and percentage of subjects) by CTC grade (1, 2, 3, 4) within treatment and total groups. When presenting results, the highest CTC grade at a post-baseline visit (including unscheduled visits) will be used. The denominator for frequency calculation is the safety analysis set.

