- c. Subjects will remain off all study drugs and should avoid initiating any new medical or non-medical therapies for MAC lung infection.
- d. Serum pregnancy testing will be performed on WOCBP at Screening. A urine pregnancy test (at least 25 mIU/mL sensitivity) must be performed for all WOCBP at all subsequent visits starting at Baseline. Women not of childbearing potential are defined as postmenopausal (ie, amenorrheic for at least 12 months), or surgically or naturally sterile.
- e. All PRO assessments will be performed prior to any other assessments (with the exception of sputum collection) and administration of study drugs and should be performed in the following order: QOL-B, PROMIS F-SF 7a, EXACT, EXACT-RS, SGRQ, FACIT-Fatigue, PGI-S-Respiratory, and PGI-S-Fatigue.
- f. Collection of data is continuous. Data will be retrieved by study staff at in-clinic visits.
- g. The physical examination will also include measurement of body weight; the measurement of height, without shoes, will only be done at Screening. All physical examinations should be performed prior to administration of study drugs.
- h. Vital signs and pulse oximetry will be assessed prior to administration of study drugs.
- i. The Baseline audiology examination must be performed during Screening or on Day 1 before administration of study drugs and evaluated by the Investigator.
- j. Tests may be performed if required by local labeling guidance; Investigators should perform all monitoring according to local label
- k. Only SAEs will be collected after the ICF is signed until Baseline.
- l. At Baseline, AEs will be assessed only after administration of study drugs. Any AE that has occurred prior to the first dose must be included in the subject's medical history, including any AEs that occur within the Screening period.

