9.3. Audiology Test

Audiology testing will be performed at study visits specified in the Schedule of Assessments (Table 4). Additional assessments may be conducted if required per local labeling guidance. Frequencies of 250, 500, 1000, 2000, 4000, and 8000 Hz will be evaluated for each ear using air conduction.

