9.9.3. Adverse Events of Special Interest

Adverse events of special interest are defined as events known to be attributed to parenteral amikacin and inhalation of antibiotics. Additional information on some AESIs will be collected in the eCRF. The AESI category groups and preferred terms include the following:

- Hypersensitivity pneumonitis (allergic alveolitis, pneumonitis, interstitial lung disease)
- Hemoptysis (hemoptysis)
- Bronchospasm (asthma, bronchial hyperreactivity, bronchospasm, dyspnea, exertional dyspnea, prolonged expiration, throat tightness, and wheezing)
- Exacerbation of underlying pulmonary disease (COPD, infective exacerbation of chronic obstructive pulmonary disease, and infective exacerbation of bronchiectasis)
 - Pulmonary exacerbation will be defined based on the Investigators best clinical judgment. Details of these events should be reported in an additional “pulmonary exacerbation” page of the eCRF.
- Ototoxicity (deafness, neurosensory deafness, unilateral deafness, dizziness, hypoacusis, presyncope, tinnitus, vertigo)
- Nephrotoxicity (nephropathy toxic, azotemia, oliguria, albuminuria, acute kidney injury, anuria, renal impairment)
- Neuromuscular disorders (muscle weakness, peripheral neuropathy, and balance disorder)

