### **6.2. Safety Analysis Set**

The safety analysis set comprises all subjects who were randomized and received at least 1 dose of ALIS, ELC, AZI or ETH.

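### The CTC hearing table counts subjects without evaluable audiograms as non-events; the exacerbation AESI misses investigator-judged events coded outside three preferred terms

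*SAP*

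**What the plan says.** **Hearing.** SAP 12.12 assigns each subject the highest CTC grade (1 to 4) found at any post-baseline visit, unscheduled visits included, and tabulates number and percentage by treatment. Three rules govern the table:

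- the reference for grading: "The baseline hearing test is the threshold for deriving the grade";
- the rows: "Subjects who do not meet any of the above CTC grades will not be summarized";
- the percentage base: "The denominator for frequency calculation is the safety analysis set".

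SAP 6.2 defines that base: "The safety analysis set comprises all subjects who were randomized and received at least 1 dose of ALIS, ELC, AZI or ETH".

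On whether testing is required, Protocol 9.3 says "Audiology testing will be performed at study visits specified in the Schedule of Assessments". Table 4 schedules audiology at Screening (footnote i also allows Day 1 before dosing, and makes this baseline test obligatory) and once after baseline, at Month 6/EOT. Footnote j is attached to the same row: "Tests may be performed if required by local labeling guidance; Investigators should perform all monitoring according to local label".

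**Exacerbation.** Protocol 9.9.3 lists three preferred terms for exacerbation of underlying pulmonary disease and adds, under the same bullet, "Pulmonary exacerbation will be defined based on the Investigators best clinical judgment", with details on a dedicated eCRF page. SAP 12.5 marks the bronchospasm and exacerbation categories as additionally categorised by the investigator and says of that categorisation: "This judgment is listed but not summarized or used for identification of AESIs". Appendix H carries the same three exacerbation terms as the protocol.

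**The concern.** A percentage of subjects with hearing impairment is normally read as an incidence. Here the base includes people for whom no grade could be derived, and the table has no row to separate them from people who were tested and found unchanged. With a single scheduled post-baseline audiogram, and a footnote that can be read as making testing optional, some missing tests are foreseeable.

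Ototoxicity and exacerbation are both prespecified AESIs, and Protocol 1.4 says ALIS has not been studied in this population and that the study will evaluate its benefit and risk there. With about 50 subjects per arm, a few untested subjects move a percentage visibly.

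For exacerbation, the protocol collects a specific investigator judgment on its own eCRF page, and the SAP then keeps it out of every summary. A judged exacerbation coded to an unlisted term is absent from the AESI category. A non-infective exacerbation of bronchiectasis is one example, and bronchiectasis is a named underlying disease in this trial.

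**Working it through.** The documents state no hearing-loss rate, no share untested and no exacerbation coding share, so there is no figure of the plan's own to reproduce. What follows shows what the counting rules do.

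**Hearing: one arm**

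Inputs:
- Arm size 50 (SAP 4.3.1).
- r = rate of any CTC grade among evaluable subjects, meaning those with a baseline and at least one post-baseline audiogram. Assumed 10%.
- m = share of the safety set not evaluable. Assumed, over a range of 0 to 30%. The 5% and 20% values also appear in SAP 4.3.1, but there they are PRO missing-data rates in the power claim, not audiology rates.

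Grades 1 to 3 are threshold shifts, so they need both tests. The reported percentage is r × (1 − m).

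| m | Reported (safety set) | Evaluable denominator |
|---|---|---|
| 0% | 10% | 10% |
| 5% | 0.10 × 0.95 = 9.5% | 10% |
| 20% | 4/50 = 8% | 4/40 = 10% |
| 30% | 0.10 × 0.70 = 7% | 10% |

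The relative shortfall equals m.

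**Hearing: between arms**

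Assumed evaluable rates are 20% on ALIS and 5% on ELC: difference 15 points, ratio 4.0.

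| m ALIS | m ELC | Reported | Difference | Ratio |
|---|---|---|---|---|
| 20% | 20% | 16.0% vs 4.0% | 12.0 | 4.0 |
| 30% | 5% | 14.0% vs 4.75% | 9.25 | 2.9 |
| 5% | 20% | 19.0% vs 4.0% | 15.0 | 4.75 |

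Equal shares leave the ratio alone and shrink the difference. Unequal shares can lower or raise the ratio.

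**Hearing: what the safety-set percentage assumes**

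Let q be the rate among subjects not evaluable. The rate in the whole safety set is r(1 − m) + q × m. The SAP's figure sets q = 0; an evaluable denominator sets q = r. With r = 10% and m = 20%, the whole-set rate lies between 8% (q = 0) and 8% + 20% = 28% (q = 1). The planned table reports the lowest value compatible with the data and does not show m, which a reader would need in order to see that.

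**Exacerbation**

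Let s be the share of investigator-judged events coded to a listed term, and c the number of subjects with a listed term but no judged exacerbation (any adverse event coded to COPD counts). Both are unknown. With 10 of 50 judged (20%, assumed) and c = 0:
- s = 100% gives 20%;
- s = 80% gives 16%;
- s = 50% gives 10%.

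With s = 80%, c = 2 brings the count back to 8 + 2 = 10 (20%), and c = 3 takes it to 11 (22%). The net direction therefore cannot be settled from the documents.

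**The case against.** **On hearing.** The table calls nobody unimpaired; read literally, it gives the share of treated subjects with a documented grade. Counts accompany the percentages, footnotes must state the percentage base, and a missing category may be added where appropriate (SAP 7.1). Audiology is also summarised by visit, frequency and ear, and n is a standard statistic. Listings are provided. Subjects who stop ALIS/ELC early are due EOT assessments at the next scheduled visit (Protocol 4.2.1), and unscheduled audiograms count. Ototoxicity is also captured as an AESI without any audiogram.

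These are real mitigations, but none corrects the CTC percentage. The by-visit n is per frequency and ear, not per graded subject, and the missing category is optional.

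**On the footnotes.** Protocol 9.3 says additional tests may follow the local label, so footnote j can be read as covering extra testing only. That reading is available, but footnote j sits on the audiology row itself and does not say so. A reader might go further and infer that testing would be skipped in countries for which the protocol lists no ALIS approval, such as South Korea. The documents do not support this: Protocol 5.1.4 ties local-label audiology monitoring to azithromycin and ethambutol.

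**On direction.** A reader might infer that the rule hides an ALIS excess. It can, but the third between-arm case above shows the opposite.

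**On the remedy.** If symptomatic subjects are tested more often, a tested-only denominator overstates the rate. That stands, and is why a not-evaluable row is needed as well.

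**On exacerbation.** It would be tempting to say that investigator-judged exacerbations are not counted. That goes too far. Those coded to a listed term are counted, other treatment-emergent ones appear in the TEAE tables by SOC and PT, the judgment is listed, the protocol names the same three terms, and SAP 12.5 allows terms to be added. The protocol's judgment sentence can also be read as guidance on diagnosis and recording rather than as the rule for counting the AESI.

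**Conclusion.** The hearing point holds. Whenever anyone lacks a baseline or post-baseline audiogram and the rate is above zero, the CTC percentage is below the rate among evaluable subjects, by a relative amount equal to the share not evaluable: nothing at 0%, 10% down to 8% at an assumed 20%, and 7% at an assumed 30%. The actual share is unknown, and the effect on the ALIS-ELC contrast can go either way. Whether the scheduled audiograms are required is not stated consistently in the protocol.

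The exacerbation point holds only narrowly: judged events coded outside the three terms drop out of the AESI category, although the protocol defines pulmonary exacerbation by that judgment. A claim that the exacerbation rate is biased downward is not supported, because COPD-coded events that are not judged exacerbations add to the count. Its size and net direction are unknown.

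Neither point touches the primary validation objective, and the safety summaries are descriptive. Both merit correction because the reported safety rates are open to misreading and the remedy is cheap.

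**What to change.** - **SAP 12.12.** Base the CTC percentages on subjects with a baseline and at least one post-baseline audiogram. Add two rows by arm: evaluable with no grade, and not evaluable. This matches the SAP's own practice in 9.3.6, where microbiology percentages use subjects with available data. Cost: SAP wording and one table shell; a slightly smaller denominator, and possible overstatement if symptomatic subjects are tested more often, which the not-evaluable row lets a reader judge.
- **Protocol 9.3 and Table 4 footnotes i and j.** Reconcile them on whether the scheduled audiograms are required. Cost: a protocol clarification.
- **SAP 12.5.** Keep the preferred-term count and add beside it a by-arm summary of investigator-judged exacerbations. Cost: one table from data already collected on the dedicated eCRF page.
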